We will provide data from the 20 sites and Find and Treat to the Health & Social Care Information Centre (HSCIC). These records will be list cleaned and then linked by HSCIC to the Hospital Episode Statistics (HES) database to provide data on hospitalisations and A&E attendances and deaths for individuals in the 20 sites and Find and Treat database. In order to be able to identify co-morbidities more accurately we will request data on all previous admissions for these groups for identification of

comorbidities but analyses of admission rates will be confined to the period November 2008 – November 2016.

Study design:

We will construct a virtual cohort that will take first date of admission as the entry point (earliest November 2008) or, for control groups an admission matched by month and year restricted to individuals over the age of 18. Exit from the virtual cohort will be at the end of November 2016 or, if earlier, date of death. We will conduct person-level analyses using Poisson regression to compare overall hospitalisation rates, emergency admission rates, all cause mortality and avoidable mortality rates in:

- 1) Homeless people using the different categories of SIHCC service (clinically led services - sites 1&2, 7-13; non-clinically led services - sites 3&4, 14-20)
- 2) Find and Treat Homeless population and sites 5&6 with standard usual care
- 3) Socially deprived non-homeless population.

We will also conduct analyses at the level of the hospital admission whereby through knowledge of the dates of SIHCC involvement and service user group we will be able to classify hospital admissions in the period November 2008- November 2016) into the following groups:

- 1) Admissions in a socially deprived non homeless population
- 2) Admissions in the general homeless population (Find and Treat data)
- 3) Admissions in homeless service users prior to their first engagement with SIHCC
- 4) Admissions in homeless service users where there is evidence of SIHCC support for that admission
- 5) Admissions in homeless service users that occur following SIHCC support but where there is no record of support for the subsequent admission.

We will use Cox regression survival models and Kaplan Meir plots (accounting for clustering at the level of the hospital and individual) to explore how admissions in these groups compare in terms of the following primary outcomes:

- 1) Time from discharge to next A&E attendance

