- 2) 28 day emergency readmission rates (these are a commonly used indicator within the NHS)
- 3) Time from discharge to next hospital inpatient readmission

Secondary outcomes we will examine include:

- 1) Time from admission to death
- 2) Duration of inpatient admission
- 3) Time from admission to mortality from causes amenable to healthcare
- 4) Time from discharge to admission with ambulatory care sensitive (ACS) conditions
- 5) Time from discharge to next planned admission,
- 6) Overall readmission rates
- 7) Unscheduled readmission rates
- 8) All cause mortality
- 9) International Classification of Diseases 10th Revision chapter-specific mortality
- 10) In-patient costs using Health Resource Group

For those service users with quality of life data we will explore how this changes following involvement of services and how it compares to the measures of quality of life derived from studies within Find and Treat service users and within socially deprived non-homeless groups.

A variety of mortality groupings have been developed to identify causes of death that could be considered avoidable through better medical care depending on age at which they occur. The proposals for the Public Health Outcome Monitoring framework take a similar approach and focus on key areas of avoidable mortality namely: mortality from suicide, communicable diseases, excess

seasonal mortality and, in persons aged less than 75 years, cardiovascular disease, cancer, chronic liver disease and chronic respiratory diseases. All of these are useful indicators within homeless populations.

Sample size:

Our sample size is based upon our estimates of historical data from the two types of SIHHC services (non-clinically led SIHHC services vs. clinically led SIHHC). We estimate that each type will have data from approximately 2,208 individuals for the two-year duration of the study, based on the services seeing on average 92 people per month.

From previous health service evaluation data on homeless groups we expect hospitalisation rates to be 0.7 episodes per person-year for homeless individuals admitted to hospital. An important reduction in readmission rates would be 10%. To undertake a sample size calculation to determine the study size required to detect such a reduction in readmission rates, the following variables were defined:

μ_0 = mean readmission rate in the baseline group = 0.7 episodes per person-year

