μ_1 = mean readmission rate in the SIHHC group = 0.6 episodes per person-year

$v=1.96$ =percentage point of the normal distribution corresponding to a 5% two-sided significance level

$u=0.84$ =one-sided percentage point of the normal distribution corresponding to (100%- type II error [FN / (TP + FN)]) at 80% power

Using the following equation we estimated minimum sample size (per group) required for comparison of two rates (readmissions per person-year):

$$\begin{aligned} & (u+v)^2 * (\mu_1 + \mu_0) / (\mu_1 - \mu_0)^2 \\ & (0.84+1.96)^2 *(0.7 + 0.6) / (0.7 - 0.6)^2 \\ & =1019 \text{ person-years per group} \end{aligned}$$

Adjustment for confounders as far as is possible within the analysis results in a doubling of sample size (additional 10% per confounder; likely 10 confounding variables). Therefore 2038 person-years are required per group. Assuming that the SIHHC clinically led and non-clinically led sites see on average 90 service users each month during the study period (which for the purposes of this calculation we have assumed this to be November 2013-November 2015 as many services may have been shut down before this time period and in some we may collect data at an earlier point) we estimate that this translates to a total 2,160 individuals at each of these two types of service.

Follow up: For the primary analysis, individuals will enter the cohort on date of first hospital admission (earliest November 2008) and will be censored at the end of the study period (November 2016) or death, whichever ever comes first.

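### The person-level Poisson rates and the sample size make no stated allowance for extra-Poisson variation or clustering by site, so the 80% power for 0.7 v 0.6 is not assured

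*Protocol*

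**What the plan says.** Protocol, Comparative Effectiveness Analysis, Study design, plans two layers of analysis.

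- **Person level.** "We will conduct person-level analyses using Poisson regression to compare overall hospitalisation rates, emergency admission rates", together with two mortality rates, across three sets of people. The first set is users of the two types of specialist service ("clinically led services - sites 1&2, 7-13; non-clinically led services - sites 3&4, 14-20"), which makes nine sites per type. No dispersion term, robust variance or site effect is mentioned.
- **Admission level.** "We will use Cox regression survival models and Kaplan Meir plots (accounting for clustering at the level of the hospital and individual") for the three primary outcomes: time to next A&E attendance, 28-day emergency readmission and time to next inpatient readmission.

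Under Sample size, the protocol says "we estimated minimum sample size (per group) required for comparison of two rates (readmissions per person-year"). The inputs are "mean readmission rate in the baseline group = 0.7 episodes per person-year" and "mean readmission rate in the SIHHC group = 0.6 episodes per person-year", with 1.96 and 0.84 for a two-sided 5% level and 80% power. The result of 1019 person-years per group is doubled to 2038, and the stated reason is about ten confounders at 10% each. About 2,160 individuals are expected at each type of service.

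**The concern.** Poisson regression with model-based standard errors takes the variance of a count to equal its mean and treats people as independent. Two features of this study work against that.

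- People differ in their propensity to be admitted, so admission counts can vary more than Poisson.
- Type of specialist service is a property of the site, so the comparison of the two types rests on nine sites against nine, however many people each site contributes.

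The protocol recognises both dependencies in its phrase "accounting for clustering at the level of the hospital and individual", but attaches it only to the Cox and Kaplan-Meier work.

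If neither is allowed for, intervals for overall and emergency admission rates are too narrow and the stated power is too high. The consequence reaches beyond the rate tables. The primary cost-effectiveness model (Health Economics Analysis) is linked to the effectiveness data and lists overall and unscheduled readmission rates among its outcomes.

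**Working it through.** **1. Reproduce the protocol's figure.** Inputs are from Sample size: rates 0.7 and 0.6, v = 1.96, u = 0.84.

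(0.84 + 1.96)² × (0.7 + 0.6) / (0.1)² = 7.84 × 1.3 / 0.01 = 1019.2; doubled, 2038.

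This is the formula for two independent Poisson rates. It reproduces exactly, so no dispersion or cluster factor is in it, and the doubling is assigned to confounders.

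**2. Baseline power.** Treat the doubling as a variance inflation of 2 at 2038 person-years:

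variance = 2 × 1.3/2038 = 0.001276; power = Φ(0.1/√0.001276 − 1.96) = Φ(0.84) = 80%, the protocol's own claim.

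**3. Extra-Poisson variation only.** Assumptions: negative-binomial dispersion k, T years per person, mean rate 0.65. The variance factor is 1 + 0.65kT. With T = 1:

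| k (assumed) | Variance factor | Person-years needed (2038 × factor) | Power at 2038 |
|---|---|---|---|
| 0.5 | 1.325 | about 2,700 | 68% |
| 1 | 1.65 | about 3,363 | 59% |
| 2 | 2.30 | about 4,687 | 45% |

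**4. Site variation only.** Assumption: residual between-site coefficient of variation CV, nine sites per group. Added variance = CV² × (0.7² + 0.6²)/9 = CV² × 0.85/9.

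| CV (assumed) | Added variance | Total variance | Power at 2038 | Power, unlimited person-years |
|---|---|---|---|---|
| 0.05 | 0.000236 | 0.001512 | 73% | near 100% |
| 0.10 | 0.000944 | 0.002220 | 56% | 90% |
| 0.15 | 0.002125 | 0.003401 | 40% | 58% |
| 0.20 | 0.003778 | 0.005054 | 29% | 37% |

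These are normal approximations; a t reference with 16 degrees of freedom would lower them somewhat. The last column shows that more person-time cannot take power past the limit set by nine sites.

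**5. Longer follow-up.** Assume an average of two years for 2,160 people, which is 4,320 person-years, and keep the doubling. Power is then 98% under pure Poisson, 77% with k = 1 and no site variation (factor 1 + 0.65 × 1 × 2 = 2.30), 72% with CV 0.10 alone and 33% with CV 0.20 alone.

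**6. Interval width.** If the true variance is 1.65, 2 or 3 times Poisson, a model-based 95% interval is too narrow by √1.65 = 1.28, √2 = 1.41 or √3 = 1.73. The error of a nominal 5% test, 2 × [1 − Φ(1.96/√factor)], is then about 13%, 17% or 26%.

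**The case against.** **The analysis half rests partly on silence.** Naming Poisson regression fixes a rate model. It does not exclude robust or clustered variance, and a statistical analysis plan could add it. A reader might infer that the protocol commits to model-based Poisson errors; it does not say so. What stands is that clustering is specified for one analysis and not for the one beside it. The sample size is also a finished calculation here, and a later plan cannot change the power it claims.

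**The primary outcomes are covered.** A reader might infer that the main results are at risk. All three primary outcomes are assigned to Cox models with hospital and individual clustering. Overall and unscheduled readmission rates are listed as secondary.

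**Adjustment may absorb part of it.** Under Confounding variables, the protocol controls for comorbidity, reason for admission and past hospital use from HES. What matters is the dispersion and site variation left after that, which may be smaller than the raw values.

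**Follow-up may exceed one year.** Entry can be as early as November 2008, with censoring in November 2016. This recovers power, as step 5 shows, but only up to the limit set by site variation.

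**The sizing contrast is not clear.** The headcounts are per service type, but the two rates are labelled as a baseline group and a specialist-care group. The nine-against-nine figures hold only on the service-type reading. The protocol also calls the comparison of service types a subgroup analysis, and says its main purpose is not to recommend one model over another.

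**Direct evidence of overdispersion is thin.** The background mention of frequent attenders concerns A&E departments, not admissions. The protocol's own allowance for individual-level clustering is better support.

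**Conclusion.** The point holds for the person-level admission rates and for the sample size. The 1019 and 2038 person-years contain no allowance for extra-Poisson variation or for site, so 80% power is not assured. On the assumed ranges it lies between about 45% and 68% for dispersion 0.5 to 2, or between about 29% and 73% for residual between-site CV 0.05 to 0.20. Each range takes one source alone, at 2038 person-years with the confounder doubling kept.

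The protocol supplies neither a dispersion nor a between-site figure. The direction is clear if any such variation remains after adjustment; the size is not established. A reader might infer that the study is underpowered by a known amount, or that false-positive findings are probable. The documents support neither. Repeat-event overdispersion applies to admission counts only; for the mortality rates, only the site point applies.

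**What to change.** - **Study design.** Extend the clustering statement to the person-level analyses. For admission counts, use negative binomial regression or Poisson regression with robust variance, with log person-time as offset; either is adequate. For all person-level rates, including mortality, add a site random effect or site-clustered variance, with a small-sample correction for nine against nine sites.
- **Sample size.** State which contrast the calculation serves. Restate the requirement and the power over a stated range of dispersion, average follow-up per person and between-site CV. This restates what the expected cohort can show and does not call for enrolling more people.

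The cost is wording and a different model call, with no new data. The downside is wider intervals and a less favourable stated power.

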Pathway approach comprises a hospital based team which is GP and nurse led. For example, the newly established Pathway Team, which works across the King's Health Partnership (KHP) hospitals (Guys and St Thomas, King's College Hospital and [to soon include] South London and the Maudsley) involves: six Homeless Health Practitioners (two general nurses and four Mental Health Practitioners); ten GP sessions per week, provided by two GP's contracted for 52 weeks per year from a local practice or urgent care centre provider; a full time social worker (employed by the hospital not the local authority); a full time housing specialist contracted from a third sector provider; a half time, band 4 secretary for administrative support; and specialist legal support from the KHP in-house legal team as necessary.

Peer support from Care Navigators is also a key component of the Pathway approach. The hospital based teams co-ordinate care for service users from hospital admission through to 'independence' (defined as 'putting service users in touch with follow-on services'). Key steps include nurse-led assessments, weekly homeless 'paper based' ward rounds and case conferences leading to multi-agency care plans. The Pathway service is structured to provide support to Accident and Emergency department staff in managing homelessness and 'frequent attenders'. Specialist intermediate care or 'medical respite' ('step down') facilities are also being developed to provide opportunities for convalescence and recuperative care.

The total annual cost of the King's Health Partners Pathway service is estimated to be £675,480. This is financed through both NHS and charitable sources. It is acknowledged that the Pathway approach is expensive and unlikely to be cost effective where there are less than 200 homeless or 'tri-morbid' admissions per annum (Pathway Annual Review, 2013, p4). As noted above, a number of areas have begun to implement the model (what has been termed 'Pathway Lite') adapting it to fit with local circumstances and available resources.

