Confounding variables: As this is a virtual cohort, we will not be able to collect a complete set of confounding variable data on individuals at entry to the study. Where data is provided by SIHHC services we will include age (year and month only), sex. As a result of the lack of baseline data will use historical HES data to determine past medical history from the age of 18 which will be used to create a variable to control for co-morbid conditions and historical hospital usage. Analyses will therefore control for age, gender, comorbidities (identified from HES data) and reason for admission, classified by Healthcare Resource Group (HRGs – groupings of treatment episodes which are similar in resource use and clinical response). Subgroup analyses will compare the different types of SIHCC services. Where provided by the SIHHC services, we will also control in subgroup analysis for medical symptoms, past use of health and social care services, mental health services, smoking, alcohol, and drug taking history, prison and homeless history, employment history.

Health Economics Analysis:

This analysis will cover three economic models. The primary analysis will be a cost effectiveness model (linked to effectiveness data described in the comparative effectiveness section). This model will take an NHS perspective, with costs based on the linked HES data analysis and outcomes based on morbidity and mortality data. Outcomes of homeless users of the two types of SIHHC service (clinically led and non-clinically led) will be compared to each other and homeless controls. Outcomes used for this analysis will include: 1. Overall hospital readmission rates; 2. Unscheduled readmission rates; 3. 28-day emergency readmission rates. Cost estimates will be calculated using national NHS

tariff data, and will include length of hospital stay, emergency admissions, and fixed and variable costs estimates for each of the SIHHC services.

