Unique Study ID created for
 Each individual record and left
 On site

Box 5: Data variables collected for WP2:**Linked HES / ONS data variables requested**

Field name (where known)	Description of contents
admidate	Date of admission
elecdate	Date of decision to admit
admimeth	Method of admission
admisorc	Source of admission
firstreg	First regular day or night admission
elecdu	Waiting time
disdate	Date of discharge
disdest	Destination on discharge
dismeth	Method of discharge
DISREADYDATE	Discharge ready date (delay in discharge)
ARRIVALDATE	Arrival date
AEATTENDCAT	Attendance category
AEATTENDDISP	Attendance disposal
TREAT2_N	treatment
APPTDATE	Appointment date
ATTENDED	Attended or did not attend
TRETSPEF	Treatment specialty
cause_of_death	Original underlying cause of death
cause_of_death_non-neonatal	Non-neonatal cause of death mentions
	Match rank (ranking of quality of match)
dod	Date of death

SIHHC data variables

Other than the demographic information, we expect few sites to contain all the data variables listed below, but where they are (and for example we know of several sites that collect EQ5D data on all service users) we will collect these unconsented data. The list below therefore provides a potential list of variables we would attempt to collect at each site.

Example field name (where known)	Description of contents
date_interviewed	Date of interview
first_name	First name
surname	Surname
middle_names	Middle names (s)
Alias	Any alias names
sex	Sex of individual
address1	Address line 1
address2	Address line 2
address 3	Address line 3
postcode	postcode

telephone	Home telephone number
mobile	Mobile telephone number
plbirth	Place of birth
ethnicity	Ethnicity
Date_admission	Date of hospital admission
Ad_diagnosis	Admitting diagnosis
Date_discharge	Date of hospital discharge
sympwloss	Currently has symptoms of weight loss for no reason
sympcough3w	Currently has been coughing for more than 3 weeks
sympfevns	Currently has fever or night sweats
symphaemopt	Currently is coughing up blood
sympsob	Currently has shortness of breath
symprone	Currently has none of these symptoms
gpyeslocal	Registered with Local GP
gpnotlocal	Registered with GP that is not local
noreggp	Not Registered to GP
ae_visits	Number of A&E visits in the last year
op_visits	Number of hospital outpatient user visits in the last year
hospitalisations	Number of hospitalizations in the last year
vaxhepb	Individual been vaccinated against Hepatitis B

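### The admission-level analysis neither restricts nor adjusts index admissions by method of admission, so a different planned/emergency mix across the five groups can leave residual confounding in the primary outcomes

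*Protocol*

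**What the plan says.** In Stage 3b of the protocol, under Comparative Effectiveness Analysis (Study design), the text states that "we will be able to classify hospital admissions in the period November 2008- November 2016) into the following groups". Four of the five groups matter most here:

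- Group 1: "Admissions in a socially deprived non homeless population"
- Group 2: "Admissions in the general homeless population (Find and Treat data"
- Group 3: "Admissions in homeless service users prior to their first engagement with SIHCC"
- Group 4: "Admissions in homeless service users where there is evidence of SIHCC support for that admission"

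Group 5 holds later admissions of scheme users for which no support is recorded. Cox models and Kaplan-Meier plots then compare the groups on time from discharge to next A&E attendance, 28-day emergency readmission, and time to next inpatient readmission. The limits given in that section are the date window and, for the virtual cohort, age over 18.

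Under Confounding variables, past HES records supply a variable for comorbid conditions and historical hospital usage, and "Analyses will therefore control for age, gender, comorbidities (identified from HES data) and reason for admission, classified by Healthcare Resource Group". Method of admission is not listed.

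Under Data sets used for WP2, the linked HES data are described as covering both emergency and planned admissions. Appendix One, Box 5 requests method of admission (admimeth) and a field described as "First regular day or night admission" (firstreg). It lists no patient-class field.

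**The concern.** Each classified admission starts a clock at discharge. The risk of A&E attendance or emergency readmission after a planned stay may well differ from the risk after an emergency stay. If the groups differ in that mix, they will differ on the primary outcomes with no scheme effect.

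The way the groups are formed makes a difference in mix plausible. An admission enters group 4 only if a scheme recorded support for it. For the Pathway model the Background describes that support as including "ward rounds and case conferences leading to multi-agency care plans". Groups 1, 2, 3 and 5 have no matching selection on type of stay. The protocol separates planned from unscheduled events among its outcomes, but not for the admission that starts the clock. At stake is whether a contrast between group 4 and a comparator group can be read as an effect of the scheme.

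**Working it through.** **The plan's own figure.** The admission-level analysis has no sample size or admission mix of its own. The nearest figure belongs to the person-level rate comparison: (0.84 + 1.96)² × (0.7 + 0.6) / (0.7 − 0.6)² = 7.84 × 1.3 / 0.01 = 1019.2, doubled to 2038.4. This reproduces the stated 1019 and 2038 person-years per group. It does not bear on this point.

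**The sections side by side.**

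| Question | What the protocol gives |
|---|---|
| Are planned admissions in the linked data? | Yes (Data sets used for WP2) |
| Are index admissions limited by method of admission? | No rule stated (Study design) |
| Is method of admission an adjustment variable? | Not listed (Confounding variables) |
| Is the field available? | Yes, admimeth (Box 5) |
| Are all groups selected the same way? | No; only group 4 requires scheme support for that admission |

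**Illustration of size.** All inputs here are assumptions, because the documents give none of them. Let e and q be the 28-day emergency readmission risk after an emergency and a planned index admission, s the planned share among comparators, and t the planned share in group 4. With no scheme effect and no adjustment, the ratio of group 4 to comparator is

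R = [(1 − t)e + tq] / [(1 − s)e + sq].

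Example: e = 0.20, q = 0.10, s = 0.20. The comparator risk is 0.8 × 0.20 + 0.2 × 0.10 = 0.18. At t = 0, R = 0.20/0.18 = 1.11. At t = 0.05, R = 0.195/0.18 = 1.08.

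Ranges of R for t from 0.05 to 0:

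| e, q | s = 10% | s = 20% | s = 30% | s = 50% |
|---|---|---|---|---|
| 0.15, 0.10 | 1.02–1.03 | 1.05–1.07 | 1.09–1.11 | 1.18–1.20 |
| 0.20, 0.10 | 1.03–1.05 | 1.08–1.11 | 1.15–1.18 | 1.30–1.33 |
| 0.20, 0.05 | 1.04–1.08 | 1.13–1.18 | 1.24–1.29 | 1.54–1.60 |

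**Direction.** If s = t, R = 1. If group 4 held more planned stays than its comparator (t = 0.20, s = 0.05, e = 0.20, q = 0.10), R = 0.18/0.195 = 0.92. Regular day or night attendances add a separate effect. Their next attendance is scheduled, so they shorten time to next inpatient readmission in whichever group holds more of them. No single direction therefore follows for all three outcomes.

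**The case against.** The strongest reply has four parts.

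1. **Silence is not a choice.** The protocol does not say that day cases or regular attendances count as index admissions, and record filters are often left to an analysis plan that is not shown. This is fair as regards day cases. It is weaker for method of admission, because the protocol itself fixes the groups, the outcomes and the covariates, and an analysis plan following that list would leave the variable out.

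2. **Case mix is already adjusted.** HRG, comorbidities and historical hospital usage will absorb part of any difference, and past use bears directly on regular attenders. This stands, and it means the crude ratios above are not estimates of the final bias. But the protocol defines HRGs by similarity of resource use and clinical response, which is not route of admission, so nothing shows that the imbalance is removed.

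3. **Scheme selection may not track urgency.** A reader might infer that schemes seldom support planned stays and that group 4 is essentially all emergency. The documents do not say so. Ward rounds and case conferences describe one model, which also assists A&E staff. Half of the 18 scheme sites are non-clinical, and no emergency-only criterion appears. Groups 3 and 5 are drawn from scheme users like group 4, so their imbalance could be smaller than that of group 1 or 2.

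4. **An emergency-only restriction changes the question.** The aims concern hospital discharge of homeless people in general. This stands, and it favours adjustment or stratification over restricting the main analysis.

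**Conclusion.** The point holds as a gap in confounding control. As written, the plan compares admissions selected by scheme contact with admissions not so selected, using linked data that include planned and emergency stays. It neither restricts nor adjusts on a field that it requests. Residual confounding in all three primary outcomes is possible.

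Its size and direction after the planned adjustment cannot be derived from the documents. The crude ratios, from 1.02 to 1.60 across the assumed inputs tabulated, show only that a moderate difference in mix could matter. A reader might set them against the 10% reduction that the protocol calls important. That figure is a reduction in readmissions per person-year, used in the person-level sample size, and is not a 28-day risk ratio, so the comparison is not like for like. Nor do the documents support saying that the primary outcomes simply compare unlike admissions, since that describes an unadjusted analysis that is not the one planned.

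**What to change.** - **Study design and Confounding variables:** add method of admission of the index admission (emergency or planned) as a covariate or stratification factor, defined identically in all five groups.
- **Regular day or night attendances:** identify them with the field already requested in Box 5, and state one rule for them that applies to every group.
- **Sensitivity analysis:** report the primary outcomes restricted to emergency index admissions in all groups.
- **Reporting:** tabulate the planned/emergency mix by group, so that the imbalance is seen and not assumed.

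The cost is protocol wording, slightly more analysis and smaller strata. The method-of-admission and regular-attendance fields are already in the data request. A separate rule for day cases may need a patient-class field that Box 5 does not list, and so an addition to the request.
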